9.1.5 Safety Follow-up Visit V9 (EOS Visit)

• All subjects, whether completing the treatment or who have withdrawn prematurely, will be followed up 4 weeks (28±4 days) after their last administration of study treatment to collect any new AEs and concomitant medications. This visit may be conducted by telephone call or as an in-clinic visit.

•

10. EVALUATION, RECORDING AND REPORTING OF AES

10.1 Definition of AEs

An AE is any untoward medical occurrence in a subject or clinical investigation subject administered a pharmaceutical product and which does not necessarily have a causal relationship with this treatment. An AE can therefore be any unfavourable and unintended sign (including an abnormal laboratory finding), symptom, or disease temporally associated with the use of a medicinal (investigational) product, whether or not related to the medicinal (investigational) product.

10.2 AE Reporting Period

The AE reporting period begins at the time the Informed Consent Form (ICF) is signed by the subject. The AE reporting period ends at the last study contact Visit 9/Week 16.

10.3 Eliciting AEs

If the subject reports an AE, it is the Investigator's responsibility to acquire sufficient information in order to assess causality. This may require additional laboratory testing, physical examinations, telephone contacts, etc.

In order to avoid bias in eliciting AEs, subjects should be asked a non-leading question, such as "How are you feeling?" It is also important to question the subject in a non-leading way about changes in their health or concomitant medication usage since their last visit. This information should be collected prior to completion of assessments at all study visits. In addition, any symptoms/conditions reported during assessments and deemed to be clinically significant by the Investigator will be assessed as AEs.

10.4 Assessing AEs

10.4.1 Intensity/Severity

The medical assessment of intensity of AEs, except changes in laboratory parameters, will be determined using the following definitions:

- Mild: The AE is easily tolerated and does not interfere with usual activity.
- Moderate: The AE interferes with daily activity, but the subject is still able to function.
- Severe: The AE is incapacitating and the subject is unable to work or complete usual activity.

The intensity of a particular AE to be recorded is the worst intensity experienced by the subject during the course of the event.

It is important to note the distinctions between severe AEs and SAEs. Severity is a classification of intensity of a specific event (as in mild, moderate, or severe myocardial infarction); however, the event itself may be of relatively minor medical significance (such

as severe headache). An SAE, however, is an AE that meets any of the regulatory specified criteria required for designation as seriousness described in Section 10.7.1 (i.e., a headache may be severe (interferes significantly with subject's usual function) but would not be classified as serious unless it met one of the criteria for SAEs).

10.4.2 Causality and Reporting

An Investigator who is qualified in medicine must make the determination of relationship to investigational product and any auxiliary medications for each AE and SAE. The Investigator should decide whether, in his or her medical judgement, there is a reasonable possibility that the event may have been caused by the investigational product.

If there is no valid reason for suggesting a relationship, then the AE/SAE should be classified as unrelated or unlikely related and an alternative suspected aetiology should be provided if available (i.e., concomitant medications, intercurrent illness/events). Otherwise, if there is any valid reason, even if undetermined or untested, for suspecting a cause-and-effect relationship between the investigational product and the occurrence of the AE/SAE, then the AE/SAE should be considered certainly, probably/likely, or possibly related with a rationale behind this assessment provided.

The following additional guidance may be helpful:

Term	Relationship		Definition
Certain	Yes	•	Event or laboratory test abnormality, with plausible time relationship to drug intake
		•	Cannot be explained by disease or other drugs
		•	Response to withdrawal plausible (pharmacologically, pathologically)
		•	Event definitive pharmacologically or phenomenologically (i.e., an objective and specific medical disorder or a recognised pharmacological phenomenon)
		•	Rechallenge satisfactory, if necessary
Probable/ likely	Yes	•	Event or laboratory test abnormality, with reasonable time relationship to drug intake
		•	Unlikely to be attributed to disease or other drugs
		•	Response to withdrawal clinically reasonable
		•	Rechallenge not required
Possible	Yes	•	Event or laboratory test abnormality, with reasonable time relationship to drug intake
		•	Could also be explained by disease or other drugs
		•	Information on drug withdrawal may be lacking or unclear
Unlikely	No	•	Event or laboratory test abnormality with a time to drug intake that makes a relationship improbable (but not impossible). Disease or other drugs provide plausible explanation
Unrelated	No	•	Event or laboratory test abnormality which is clearly related to circumstances not connected with the drug intake

If the causal relationship between an AE/SAE and the investigational product is determined to be "certain", "probable/likely", or "possibly" related, the event will be considered to be related to the investigational product for the purposes of expedited regulatory reporting. In circumstances where the causal relationship has not been provided, the event will be considered as related and qualify for expedited regulatory reporting.

10.4.3 Outcome Categorisation

Outcome may be classified as: recovered/resolved (i.e., without sequelae); recovered/resolved with sequelae; recovering/resolving; not recovered/not resolved; fatal; or unknown (if follow-up is not possible).

If the outcome of an SAE is reported as recovered/resolved with sequelae, the Investigator should specify the kind of sequelae on the SAE form. If the outcome of an SAE is reported as unknown, the Investigator should specify (on the SAE form) the rationale why unknown was selected.

"Fatal" should be recorded as an outcome when the AE results in death. If more than 1 AE is possibly related to the subject's death, the outcome of death should be indicated for the AE that, in the opinion of the Investigator, is the most plausible cause of death. All other ongoing AE/SAEs will be recorded as not recovered/not resolved at the time of death.

In case of a fatal outcome, the Investigator should provide a working diagnosis (event which caused outcome, e.g., death due to fatal myocardial infarction) instead of reporting only death; and an autopsy report should be provided where possible. If the cause of death later becomes available (e.g., after autopsy), this working diagnosis should be replaced by the established cause of death.

Although "fatal" is usually an outcome of an event, events such as sudden death or unexplained death should be reported as SAEs.

10.5 Recording and Reporting

10.5.1 Persistent or Recurrent AEs

AEs that extend continuously, without resolution, between trial assessments should only be recorded once in the eCRF. The initial severity of the event should be recorded, and the severity should be updated to reflect the most extreme severity any time the event worsens.

AEs that resolve and subsequently recur should have each recurrence recorded separately in the eCRF.

All AEs persisting at the time of study completion will be followed by the Investigator through contact with the subject until resolution or stabilisation, or the subject is lost to follow-up and cannot be contacted. The outcome must be documented in the subject's source documents.

10.5.2 **Diagnosis Versus Signs and Symptoms**

Where possible, the Investigator should report a diagnosis rather than individual signs and symptoms or abnormal laboratory values. However, if a constellation of signs and/or symptoms cannot be medically characterised as a single diagnosis or syndrome at the time of reporting, each individual event should be recorded in the eCRF. If a diagnosis is subsequently established, all previously reported AEs based on signs and symptoms should be nullified and replaced by 1 AE report based on the single diagnosis, with a starting date that corresponds to the starting date of the first symptom of the eventual diagnosis.

The Investigator should use standard medical terminology/concepts; avoid colloquialisms and abbreviations. Only 1 AE term should be recorded in each event field in the eCRF.

Pre-existing Medical Conditions 10.5.3

A pre-existing medical condition is one that is present at the screening visit for this study. Such conditions should be recorded on the medical history eCRF. A pre-existing medical condition should be recorded as an AE only if the frequency, severity, or character of the condition worsens during the study. When recording such events on the AE eCRF, it is important to convey the concept that the pre-existing condition has changed by including applicable descriptors (e.g., "more frequent headaches").

10.5.4 Clinical Laboratory Evaluations

The intensity of changes in clinical laboratory parameters should be determined according to the FDA guidance for Industry, Toxicity Grading Scale for Healthy Adult and Adolescent Volunteers Enrolled in Preventive Vaccine Clinical Trials [14] provided in Appendix 2.

Not every laboratory abnormality qualifies as an AE. It is the Investigator's responsibility to review all laboratory findings. Medical and scientific judgment should be exercised in deciding whether an isolated laboratory abnormality should be classified as an AE. When evaluating such changes, the criteria below and the extent of deviation from the reference range, the duration until return to the reference range, either while continuing treatment or after the end of treatment with the investigational product, and the range of variation of the respective parameter within its reference range, must be taken into consideration:

- Is accompanied by clinical symptoms.
- Results in a change in study treatment (e.g., dosage modification, treatment interruption, or treatment discontinuation).
- Results in a medical intervention (e.g., potassium supplementation for hypokalaemia) or a change in concomitant therapy.

- Presents shift of a parameter from a normal value to a pathological value, or results in a deterioration of FDA Toxicity grade [14], or a further worsening of an already pathological value.
- Is clinically significant in the Investigator's judgement.

It is the Investigator's responsibility to review all laboratory findings. Medical and scientific judgement should be exercised in deciding whether an isolated laboratory abnormality should be classified as an AE. When evaluating such changes, the extent of deviation from the reference range, the duration until return to the reference range, either while continuing treatment or after the end of treatment with the investigational product, and the range of variation of the respective parameter within its reference range, must be taken into consideration.

If, at the end of the treatment phase, there are pathological laboratory values which were not present at baseline, further clinical or laboratory investigations should be performed until the values return to within reference range or until a plausible explanation (e.g., concomitant disease) is found for the pathological laboratory values.

The Investigator should decide, based on the above criteria and the clinical condition of a subject, whether a change in a laboratory parameter is clinically significant and therefore represents an AE. If the Investigator considers such an AE as serious (e.g., medically significant event fulfilling criteria per Section 10.7.1), it must be reported as an SAE.

If a laboratory abnormality meeting the above criteria is a sign of a disease or syndrome only the diagnosis should be recorded in the eCRF.

If a laboratory abnormality meeting the above criteria is not a sign of a disease or syndrome, the abnormality itself should be recorded in the eCRF, along with a descriptor indicating if the test result is above or below the normal range (e.g., "elevated potassium," as opposed to "abnormal potassium").

If the laboratory abnormality can be characterised by a precise clinical term per standard definitions, the clinical term should be recorded as the AE; for example, hypercalcaemia or hypoglycaemia. Observations of the same laboratory abnormality from visit to visit should not be repeatedly recorded in the eCRF, unless the aetiology changes. The initial severity of the event should be recorded, and the severity or seriousness should be updated any time the event worsens.

All pathological laboratory findings/values diagnosed throughout the treatment period should be reviewed by the Investigator to provide a final clinical assessment in view of the dynamic of laboratory changes/abnormalities.

10.5.5 Worsening of the Disease Under Study

Symptoms and signs of the disease under study should not be considered AEs as long as they are not regarded as worsening of the clinical features of the disease under study. If a sign or symptom of the disease has unexpectedly worsened in severity or frequency or changed in nature at any time during the study, the symptoms and signs should be recorded as AEs, and clearly marked as worsening of the signs or symptoms in the eCRF.

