- In case any subject warrants medical care during the course of the study, the Investigator will be permitted to prescribe treatment(s) at his/her discretion, in order to protect the subject's safety and well-being and according to acceptable standards of medical care.

Any concomitant treatment given for any reason during the course of the study must be recorded on the eCRF and in the subject's medical records, including dosage, start and stop dates and reason for use.

RISKS/PRECAUTIONS 7.

7.1 **Special Warnings and Precautions for Use**

The safety and tolerability and preliminary efficacy of multiple doses of VIT-2763 in adult and adolescent patients with NTDT and documented iron overload will be investigated in this Phase 2a clinical trial.

The results of a Phase 1 clinical trial in healthy subjects revealed that treatment with single oral doses of VIT-2763 ranging from 5 mg to 240 mg and 7-day treatment with VIT-2763 oral doses of 60 mg QD, 120 mg QD, 60 mg BID and 120 mg BID was well tolerated and no SAEs were reported and no discontinuations due to AEs were reported. There were also no findings of clinical relevance with respect to vital signs, 12-lead ECG, telemetry or physical examination. With limited clinical data about previously observed adverse reactions from human studies being available, no serious adverse drug reactions (ADRs) are considered expected by the Sponsor for the purpose of expedited safety reporting of SUSARs and annual/aggregate safety reporting though.

Based on the known pharmacology, nonclinical studies including repeated dose toxicity data, and the available clinical data in adult healthy volunteers to date with VIT-2763, no safety concern is expected for the intended use in a paediatric population of adolescents (12 years and above) for a 3-month treatment duration.

Excessive doses of VIT-2763 could cause acute hypoferraemia. Based on nonclinical data, ECG monitoring is recommended, and standard emergency treatment should be applied. Caution should be exercised in subjects with:

- Developing iron deficiency during treatment.
- A Grade 4 anaemia including Hb < 8.0 g/dl (5.0 mmol/l) for female subjects or < 8.5 g/dl (5.3 mmol/l) for male subjects, and with an absolute Hb drop from baseline >2 g/dl for males and females, according to FDA toxicity grading scale for healthy adult and adolescent volunteers [14].

Based on the nonclinical safety findings, caution should be exercised in subjects with:

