8.1.2 Symptoms and Signs of Anaemia

The Investigator must assess signs and symptoms associated to anaemia in β -thalassaemia:

- Fatigue, weakness
- Shortness of breath
- Pale or yellowish skin
- Deformities of the facial bones
- Slow growth, growth retardation
- Abdominal swelling
- Dark urine

Any new clinically relevant symptom or sign of worsening of β -thalassaemia associated anaemia, or any other comorbidity, as assessed by the Investigator, must be reported as an AE (see Section 10).

The β-thalassaemia associated genotype, clinical presentation and RBC transfusion needs received during the past 24 weeks prior to randomisation which are part of the inclusion criteria, must be documented in the source data (see Section 5.2).

Physical Examination and Vital Signs 8.1.3

The body systems to be assessed in the physical examination include general appearance, head (eyes, ears, nose and throat), cardiovascular, respiratory, abdominal, musculoskeletal, neurological, lymph nodes, and skin. In the study, physical examination is performed at screening Visit V1 (i.e., Day -28 to -1) and on Visit V3 (Day 1), and V8 (Day 84). Facultative physical examinations can be performed on indication, i.e., symptom-directed, on all other visits.

Vital signs measurements include diastolic blood pressure, systolic blood pressure, and pulse rate. Vital signs are assessed at screening Visit V1 and on Visits V3 to V8. Vital signs should be performed at V3 to V8 before IMP dosing, after a resting period of at least 5 minutes. Any new clinically relevant change as assessed by the Investigator, in blood pressure readings, pulse rhythm or rate must be reported as an AE (see Section 10).

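### Protocol Sections 8.1.2 and 10.5.5 set different thresholds for recording worsening of thalassaemia as an AE, so foreseeable non-serious symptomatic worsening can be missing from the AE component of the primary endpoint

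*Protocol*

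**What the plan says.** Protocol Section 8.1.2 lists signs and symptoms of anaemia in thalassaemia, among them fatigue, weakness and shortness of breath. Its reporting rule opens "Any new clinically relevant symptom or sign of worsening of" the thalassaemia and continues "associated anaemia, or any other comorbidity, as assessed by the Investigator, must be reported as an AE", with a reference to Section 10.

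Within Section 10, the rule specific to the disease under study is 10.5.5. Its first sentence begins "Symptoms and signs of the disease under study should not be considered AEs as long as they are not regarded as worsening". Its second sentence gives the recording instruction, which applies "If a sign or symptom of the disease has unexpectedly worsened in severity or frequency or changed in nature at any time during the study".

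Section 10.5.3, on conditions present at screening, says: "A pre-existing medical condition should be recorded as an AE only if the frequency, severity, or character of the condition worsens during the study". It has no expectedness test.

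The primary endpoint (Section 3.4.1) has three parts: AEs by SOC, PT, severity and relationship; SAEs in the same form; and changes in vital signs, laboratory safety tests including haematology, ECG and physical examination. Section 7.1 advises caution in subjects with "Developing iron deficiency during treatment" and in those with Grade 4 anaemia.

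**The concern.** The trial's primary objective is safety and tolerability, so the rule that decides what counts as an AE is part of the endpoint definition. Section 8.1.2 sends the investigator to Section 10, and the disease-specific rule found there is narrower on its face. The qualifier *unexpectedly* is not defined for the course of the disease. The protocol defines *unexpected* only against the Reference Safety Information, for SUSARs (Sections 10.6.2 and 10.7.3).

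The drug limits iron for erythropoiesis (Section 1.2.1), and the protocol itself provides for iron deficiency and Grade 4 anaemia (Sections 5.4.2 and 7.1). An investigator could reasonably call more fatigue with a falling haemoglobin foreseeable, either from the mechanism or from the disease. If sites resolve the conflict differently, AE incidence depends partly on site practice. The Safety Review Team also uses AE data when it advises on enrolling adolescents (Synopsis, study committees).

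**Working it through.** The plan gives no AE rate or other figure tied to this rule, so there is nothing to reproduce. The check is to apply each rule to one case: fatigue that increases on treatment, is non-serious, is judged clinically relevant, and is regarded by the investigator as foreseeable.

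| Protocol section | Test | Result for this case |
|---|---|---|
| 10.1 | Untoward occurrence; no expectedness test | Meets the AE definition |
| 8.1.2 | New and clinically relevant, in the investigator's judgement | Must be reported |
| 10.5.3 | Condition present at screening has worsened | Recordable |
| 10.5.5, first sentence | Not an AE unless regarded as worsening | Not excluded |
| 10.5.5, second sentence | Unexpectedly worsened, or changed in nature | Not required |
| 10.7.1 | Worsening of a pre-existing condition that meets a seriousness criterion | Does not apply; would apply if serious |

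The outcome depends on which section the investigator follows. The SAP does not settle it: its treatment-emergent definition (Section 5.7.1) works on AEs already recorded and cannot recover one that was never entered.

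**What is captured anyway.** Haemoglobin is a listed haematology parameter (SAP Appendix A). It is summarised as value and change by visit in the safety set, with shift tables (Protocol 12.8.1; SAP 5.7.2), whether or not an AE exists. These summaries carry no symptom, severity or causality information. The shift tables use low, normal and high categories, while entry requires mean haemoglobin of at most 11 g/dl. On the toxicity scale in Protocol Appendix 2, 11 g/dl is already graded abnormal in both sexes. If the central laboratory's ranges are similar (an assumption; none are given), most subjects start low and a further fall appears as low to low. Mean change by visit would still show it.

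**Weight of one subject.** Cohort I plans at least 20 subjects at 8:8:4 (Protocol 12.3).

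- Minimum: 8 per active arm, 1/8 = 12.5 percentage points.
- If all of about 36 randomised subjects were adults (assumption): 36 × 8/20 = 14.4 per active arm, 1/14.4 = 6.9, about 7 points.

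This is the weight of one missing subject in a given preferred term, not an estimate of under-recording. It applies only if that subject has no other event under the same term, because SAP 5.7.1 counts a subject once per term.

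**Illustration of under-recording (all values assumed).** If a share f of true worsening goes unrecorded equally in both arms, the observed risk difference is (1 − f) × the true difference. For true risks of 30% and 10%, the true difference is 20 points:

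- f = 0.25: 0.75 × 20 = 15 points
- f = 0.50: 0.50 × 20 = 10 points
- f = 0.75: 0.25 × 20 = 5 points

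The same shrinkage applies if placebo has the higher risk, and an f that differs by arm could move the difference either way.

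**The case against.** The strongest reply is that an event is lost only if the investigator relies on one adverb and passes over several other rules. Section 10.3 has clinically significant symptoms reported during assessments assessed as AEs. Section 10.5.3 covers any condition present at screening, which includes thalassaemia. Section 10.5.4 lists accompanying symptoms and further worsening of an already pathological value among the criteria to weigh for a laboratory AE. Section 8.1.6 makes a clinically relevant worsening that prompts a change of concomitant treatment an AE. Section 10.5.5 never says that expected worsening is not an AE, and it may be meant as worsening beyond the usual disease course, which would include drug-induced worsening.

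Much of this stands and limits the point. A reader might infer that worsening anaemia drops out of the primary endpoint. It does not: haemoglobin and physical examination changes are primary in their own right, and serious worsening is an SAE with no expectedness test.

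A reader might also infer a bias that hides on-target harm in the active arms. The documents do not support a direction. The protocol's hypothesis is that iron restriction raises haemoglobin (Sections 1.1 and 1.2.1), Section 7.1 does not describe anaemia as an expected effect at study doses, and the analysis is descriptive with no tests between groups.

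The reply does not remove the conflict. The other routes rest largely on judgement, and 10.5.4 continues that when an abnormality is a sign of a disease only the diagnosis is recorded, which here may lead back to 10.5.5. After baseline, physical examination is scheduled only at Visit 8 (Section 8.1.3), and the SAP only lists its findings (Section 5.8).

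**Conclusion.** The inconsistency is real and should be corrected, within narrow limits. Sections 8.1.2 and 10.5.5 give different thresholds for the same event, and 10.5.5 is incomplete in itself, since it neither excludes nor requires the recording of expected worsening. What can go missing is non-serious symptomatic worsening that an investigator regards as foreseeable, and only from the AE component of the primary endpoint.

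Neither the amount of under-recording nor its direction can be derived from the documents. In arms this small, the 12.5 or roughly 7 points carried by one subject are enough to alter how a descriptive AE table reads. The first figure rests on the planned minimum cohort, the second on the assumption that every subject is an adult.

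**What to change.** Reconcile the two sections to one recording rule. Delete *unexpectedly* from the second sentence of 10.5.5 and add a cross-reference to the 8.1.2 standard, namely worsening that the investigator judges clinically relevant. The cross-reference is needed because 10.5.5 has no relevance threshold of its own. Expectedness stays with the Reference Safety Information assessment in 10.6.2, where the protocol already handles it.

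This concerns recording only and changes no dose, stopping rule or treatment. The cost is a short text change through the amendment route in Section 16.2, a note in AE training, and a few more AE records.
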